4. INDEPENDENT REVIEW PROCESS

The independent reviewers will consist of a minimum of three qualified, board-certified radiologists with specific expertise and skills in liver MRI and liver interventional procedure. Detailed CVs will be provided by the independent readers.

All assessments performed by the independent reviewers will be captured in an audit trail in keeping with International Conference on Harmonization (ICH) guidelines for Good Clinical Practice (GCP) and Food and Drug Administration (FDA) 21 Code of Federal Regulations (CFR) Part 11.

4.1 Sequence of MRI Scans

According to the study protocol, each patient will undergo up to 3 chemoembolization treatments in both arms. MRI will be performed at baseline and at 3 timepoints post-baseline, according to the following schedule:

MRI examination #1: Baseline (Timepoint 0)
Within 1 month of the first TACE cycle(week -4 to week 0)

MRI examination #2: Timepoint 1
4 weeks after the first TACE cycle (± 1 week)

MRI examination #3: Timepoint 2
4 weeks after the second TACE cycle (± 1 week)

MRI examination #4: Timepoint 3
4 weeks after the third TACE cycle (± 1 weeks)

The protocol requires the second TACE cycle to be performed in all patients 8 weeks (\pm 2 weeks) after the initial TACE cycle, unless the investigator deems further treatment unsafe for the patient, and regardless of the response assessment performed by the independent readers. In contrast, the third TACE cycle will only be done for patients with MRI results after the second TACE cycle that demonstrate less than complete response (CR), as interpreted by the central reviewers according to modified RECIST criteria.

Therefore, the study requires that the central imaging review site provides the investigator site with the response assessment recorded for a given subject after the third MRI examination (the second post-baseline MRI examination).

4.2 Sequence of Radiology Review for Overall Response Assessment

This analysis will focus on the assessment of the secondary endpoint of overall objective tumor response. Because of the need to provide the investigational site with a timely response assessment for a given subject after the third MRI examination (the second post-baseline MRI examination which follows TACE cycle 2), images will be read consecutively as they are transferred to the central review site.

Each subject's baseline and all other imaging timepoints will be independently read in a blinded fashion by two board-certified radiologists (double read by two primary radiologists). The two primary independent radiology reviewers will be responsible for performing quantitative and qualitative assessments of imaging data of a given subject according to the modified RECIST guideline for HCC and the "Image Interpretation Guidance Manual" provided.

The primary radiology reviewers will first assess baseline imaging in order to determine the overall tumor burden and use this as a comparator for subsequent measurements. These assessments will then be locked. Changes to previous forms will not be permitted.

The same primary radiology reviewers who have assessed baseline images will then review post-baseline timepoints as soon as these images are transferred to the central imaging site. Required calculations for the sum of the longest diameters and percent changes from baseline and/or nadir (smallest recorded sum of the longest diameters) will be made automatically by the application. These assessments will then be locked. Changes to previous forms will not be permitted.

Agreement between the first and second radiologists will be determined by comparison of the overall tumor response determinations on a timepoint basis, including the following categories: (1) complete

response, 2) partial response, 3) stable disease, 4) progressive disease, or 5) unknown. Should the assessment for a given case be discordant, the case will be considered in disagreement.

If disagreement between the two primary readers is identified at any timepoint, a third reviewer will be presented with the results of the first and second readers and, as adjudicator, will determine the final assessment for the case. The adjudicator will not provide an independent assessment but must agree with an assessment of one of the two primary reviewers. The review process and the adjudication strategy are illustrated in Figure 1 below.

[figure not shown]

Figure 1. Synopsis of image data flow and adjudication strategy.

Information regarding the response classification of a given subject after the second TACE cycle (either after the agreement of both primary readers or following adjudication) will be forwarded to a sponsor data manager, who will forward the information to the investigator at the site since this information will determine eligibility for the third TACE cycle in case of less than overall CR.

Overall objective response will be calculated by the sum of complete responses and partial responses recorded at the last available assessment.

4.3 Radiology Review for Regional Response Assessment

This analysis will focus on the assessment of the secondary efficacy endpoint of objective response in the treated area (ORR-T). This is defined as the tumor response observed in the liver territory that has actually been treated with chemoembolization. This analysis will be performed after the completion of the radiology review for the overall tumor response assessment for a given subject.

The same primary readers who have assessed a given subject for the endpoint of overall tumor response will be presented with the images obtained at baseline and at post-baseline timepoint 1 as well as with the locked forms completed at the time of that analysis. Changes to the forms completed in that review will not be permitted.

Then, the primary readers will be presented with a blinded form, completed by the interventional radiologist who has performed the TACE procedure, describing the arterial vascular anatomy of the subject with identification of the arterial branches that were embolized during the treatment.

The independent radiologist will mark each lesion identified during the previous analysis as located within the treated territory or in an area of the liver parenchyma that was not embolized. This assessment will be performed for target lesions, non-target lesions, and new lesions and will lead to the assessment of the secondary endpoint of regional objective response rate as the sum of complete and partial responses observed in the treated territory.

References

Llovet JM, Di Bisceglie AM, Bruix J, et al; Panel of Experts in HCC-Design Clinical Trials. Design and endpoints of clinical trials in hepatocellular carcinoma

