11.5.2 Objective Response Rate

A secondary efficacy outcome is the Objective Response Rate (ORR). For purposes of this analysis tumor response will be based on the last post TACE liver MRI response recorded for each patient, as determined by the Central Reviewers based on mRECIST criteria. The ORR will be calculated for the ITT Population as the number of patients with a confirmed complete or partial response (based on mRECIST criteria) divided by the number of ITT patients [ORR=(# CR + # PR)/total # patients]. Patients who have discontinued from the study prior to their first post

baseline tumor evaluation will be considered to have progressed for purposes of calculating the ORR for the ITT population. Ninety-five percent confidence intervals will be calculated for the ORR for both treatment groups and for the difference between treatments. The ORR and corresponding 95% confidence intervals will also be calculated for the Evaluable Population. The ORR efficacy analysis will be performed on a locked database that will be unblinded only after all patients have completed the protocol specified treatment phase of the investigation. Treatment comparisons of the ORRs will be performed using Fisher's Exact Test.

In order to assess the robustness of the ORR analysis using the last post TACE MRI response, a sensitivity analysis of the ORR data using the first post TACE MRI response for the ITT population will be performed. In addition, a data poolability analysis will be performed using a multiple logistic regression model including factors for treatment group, investigational site, and an interaction term for treatment group and investigational site for the ITT population. For purposes of this analysis, sites enrolling fewer than 10 patients may be pooled into a single site.

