11.5.5 Objective Response Rate for Treated Area of the Liver

An analysis of objective response rate (ORR) will be performed based on the Central Reviewers' assessment of response in the treated areas of the liver only based on data from the protocol specified treatment phase of the investigation. The analysis of this outcome will employ similar methods as the overall analysis of objective response.

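### Radiology Charter 4.3 shows the treated-area (ORR-T) readers only baseline and first post-TACE images, while 11.5.5 read with 11.5.2 implies scoring at the last MRI; the two must be reconciled before unblinding

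*Combined protocol and SAP*

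**What the plan says.** ORR-T is a secondary objective (protocol section 2.b.v). It departs from overall ORR in one respect: new growth in liver not previously treated does not count as progression, while growth in the treated area, or extrahepatic spread, does.

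**Radiology Charter 4.3** describes the reading. The timing is stated: "This analysis will be performed after the completion of the radiology review for the overall tumor response assessment for a given subject". The readers are "presented with the images obtained at baseline and at post-baseline timepoint 1". They are also handed the forms that were locked in the overall review. They then receive a form from the operator showing which arterial branches were embolized. Finally, "The independent radiologist will mark each lesion identified during the previous analysis as located within the treated territory" or outside it, and this covers target, non-target and new lesions. Charter 4.1 defines timepoint 1 as the MRI 4 weeks (± 1) after the first TACE cycle.

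**Protocol 11.5.5** describes the analysis. It concerns "response in the treated areas of the liver only based on data from the protocol specified treatment phase of the investigation", and adds: "The analysis of this outcome will employ similar methods as the overall analysis of objective response".

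**Protocol 11.5.2** supplies those methods: "tumor response will be based on the last post TACE liver MRI response recorded for each patient". The first post-TACE MRI is used there only for a sensitivity analysis. Charter 4.2 agrees, computing overall response at the last available assessment.

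**The concern.** The Charter's image list stops after cycle 1, while the analysis section points to the end of treatment. Availability does not explain the difference, because the regional review starts only once the subject's overall review is finished and every scan has been read.

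The endpoint depends on where lesions sit. Under the Image Interpretation Guidance Manual (Appendix G), a new lesion means progression whatever the other lesions do. If a patient's target lesions have responded but a new lesion appears at the last MRI, the inside/outside mark on that lesion decides whether the patient is an ORR-T responder. If the lesion first appeared on MRI 2 or 3, the readers must make that mark without an image that shows it.

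If ORR-T were instead scored at timepoint 1, it would describe one cycle of treatment and ORR up to three. A gap between the two rates could then reflect timing rather than disease outside the treated territory. If the matter is left open, the choice of scan could be made after treatment assignments are known.

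**Working it through.** **Inputs** (protocol, Treatment and Assessment; sections 7.2 to 7.7): 8 ± 2 weeks between cycles; 4 ± 1 weeks between lobes in bilobar disease; MRI 4 ± 1 weeks after the last embolization of a cycle. In bilobar disease the 8 weeks run from the second lobe of the preceding cycle.

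**Formula:** time of an MRI after first TACE = sum of the intervals up to it; its window = sum of the individual windows.

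**The plan's own figure.** The protocol puts the objective response assessment at 15-25 weeks (unilobar) and 24-40 weeks (bilobar).
- Unilobar, third MRI: (8 ± 2) + (8 ± 2) + (4 ± 1) = 20 ± 5 = 15-25 weeks.
- Bilobar, third MRI: (4 ± 1) + (8 ± 2) + (4 ± 1) + (8 ± 2) + (4 ± 1) + (4 ± 1) = 32 ± 8 = 24-40 weeks.

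Both reproduce exactly, so the stated ORR timing is that of the MRI after cycle 3.

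**The other timepoints.**
- Unilobar, timepoint 1: 4 ± 1 = 3-5 weeks.
- Unilobar, timepoint 2: (8 ± 2) + (4 ± 1) = 12 ± 3 = 9-15 weeks.
- Bilobar, timepoint 1: (4 ± 1) + (4 ± 1) = 8 ± 2 = 6-10 weeks.
- Bilobar, timepoint 2: (4 ± 1) + (8 ± 2) + (4 ± 1) + (4 ± 1) = 20 ± 5 = 15-25 weeks.

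| MRI | Unilobar (weeks) | Bilobar (weeks) |
|---|---|---|
| Timepoint 1 (listed in Charter 4.3) | 3-5 | 6-10 |
| Last MRI if treatment ends after cycle 2 | 9-15 | 15-25 |
| Last MRI after cycle 3 | 15-25 | 24-40 |

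Within each disease type, timepoint 1 does not overlap the last MRI of anyone treated beyond cycle 1. The two coincide only when timepoint 1 is the patient's sole post-baseline MRI. Section 7.4 requires a second cycle unless the investigator judges it unsafe, so such patients should be the exception.

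**What the Charter's materials allow at the last MRI.**
- *Lesion visible at baseline or timepoint 1:* it can be located on the images shown. Its mark can be carried to later locked measurements if the forms hold lesion-level data for those timepoints.
- *Lesion first seen on MRI 2 or 3:* it falls within the instruction to mark every lesion but appears on none of the images listed. The documents do not say whether the locked forms record its position.
- *Territory first embolized in cycle 2 or 3:* this depends on whether the operator's form covers all cycles, which is not stated. Appendices C and E prefer selective embolization of second- or third-order branches, so later cycles may reach new territory.

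The documents give no expected ORR-T rate and no frequency of late new lesions, so the effect on the rate or on the arm comparison cannot be calculated.

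**The case against.** The strongest reply is that Charter 4.3 supplies more than two sets of images. Under Charter 4.2 the overall review reads every timepoint and locks each assessment. The regional review follows it, receives the locked forms, and marks each lesion found. A lesion's position does not change between scans, so one mark can serve all timepoints, and the images may be there only to relate lesions to the arterial map.

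Much of this stands, and it rules out several stronger conclusions that a reader might draw:
- *That ORR-T cannot be computed as planned.* This is not shown. If the forms carry lesion-level data, last-MRI scoring is feasible for lesions visible by timepoint 1.
- *That ORR-T is scored from those two scans alone.* Charter 4.3 lists images to be presented. It names no scoring timepoint, and the locked forms are also in hand.
- *That no territory mark exists for MRI 2 or MRI 3.* The instruction covers every lesion from the completed review.
- *That territory first embolized in a later cycle never counts as treated.* The form is not restricted to cycle 1, and in bilobar disease both lobes are embolized within cycle 1 (section 7.2).
- *That 11.5.5 itself prescribes the last MRI.* It asks for similar methods; the last-MRI rule comes through 11.5.2.

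The reply does not cover lesions first seen after timepoint 1. For these, Charter 4.3 conflicts with its own instruction to mark new lesions. Nor does any text describe joining marks to later measurements. If the timepoint 1 wording is a drafting slip, it still needs correcting, because the readers will work from it.

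**Conclusion.** Charter 4.3 is wrong as written. Its image list does not support the marking it requires, and it does not match the scan implied by 11.5.5 read with 11.5.2 and Charter 4.2. The mismatch concerns every patient with more than one post-baseline MRI, and the scans at issue do not overlap in time (3-5 against 9-15 or 15-25 weeks unilobar; 6-10 against 15-25 or 24-40 weeks bilobar). The risk of misclassification is narrower: it falls on patients with lesions first seen at MRI 2 or 3 and, depending on the form, on those with territory first embolized after cycle 1.

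This rests on two assumptions: that similar methods in 11.5.5 includes the 11.5.2 timepoint, which is the natural reading, and that patients follow the protocol windows. If ORR-T was meant as a timepoint 1 endpoint, nothing says so, and it would then not be comparable with last-MRI ORR. The consequence is confined to a secondary endpoint; overall survival is unaffected.

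**What to change.** Before unblinding:

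1. Amend Charter 4.3 so that the same readers see baseline and all post-baseline timepoints when marking lesions, together with a cumulative, per-cycle record of the embolized territory.
2. State in 11.5.5 that ORR-T is scored at the last post-TACE MRI, with the first post-TACE MRI as the sensitivity analysis, as 11.5.2 already does for ORR.

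If the sponsor does intend a timepoint 1 endpoint, 11.5.5 should say so and note that the result is not comparable with ORR.

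The cost is Charter and protocol wording, an operator form that identifies the cycle, and some extra marking time for the same readers. No new scans or readers are needed, and the locked overall-response forms stay as they are.

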 - iii. 20% decline from any value at screening
 2. Neutropenia
 3. Alopecia
 4. Hyperpigmentation
 5. Mucositis
- iii. Evaluate Resource Utilization as assessed by:
 1. Length of stay in hospital following each TACE procedure
 2. Number of unscheduled hospitalizations
 3. Length of stay of unscheduled hospitalizations
 4. New or increased use of non-OTC pain medications
 5. New or increased use of antibiotic medications
- iv. Evaluate overall adverse event rates between the treatment groups
- v. Evaluate objective response rates as determined by mRECIST criteria in the treated area (ORR-T)
 1. In this evaluation progression is defined as new/continued tumor growth in the treated area(s) of the liver or extrahepatic spread. New

tumor growth within an area of the liver not previously treated will not be considered progression.

c. Tertiary Objectives

1. Evaluate Time to Untreatable Progression defined as hepatocellular cancer for which further localized treatment by resection, percutaneous ablation, or embolization is not an option, or when there is extrahepatic spread of the cancer

Untreatable progression will be determined by the Central Reviewers during the study treatment and protocol-specified treatment follow up visits. After the final study TACE and associated assessments, untreatable progression will be determined by the treating physician during survival surveillance

2. Explore the relationship between pharmacokinetic (PK) data and patient outcomes including survival, tumor response, and adverse events

3. Inclusion Criteria

Patients must meet all of the following inclusion criteria in order to be entered into the study:

- a. Age 18 or older
- b. Patient has signed informed consent
- c. Patient must have a diagnosis of hepatocellular cancer confirmed by at least one of the following:
 - i. Histological confirmation
 - ii. Magnetic resonance imaging (MRI) result with early enhancement and delayed enhancement washout of at least one solid liver lesion > 1 cm. Patient must also have evidence of cirrhosis or have chronic hepatitis B.
 - iii. Contrast enhanced computed tomography (CT) with early enhancement and delayed enhancement washout of at least one solid liver lesion > 1cm. Patient must also have evidence of cirrhosis or have chronic hepatitis B.
- d. Patient must not be suitable for treatment by resection or percutaneous ablation at time of study entry.

Patients not suitable for ablation due to lesion location may be enrolled

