7.4 Second TACE Cycle

A second TACE cycle is required for all patients, unless the investigator deems further treatment unsafe for the patient. The second TACE cycle must be within 8 weeks (± 2 weeks) of first TACE cycle.

If the patient has bilobar disease, the first lobe of the second TACE cycle must undergo chemoembolization within 8 weeks (± 2 weeks) of the second lobe in the first TACE cycle, and the second lobe of the second TACE cycle must undergo chemoembolization within 4 weeks (± 1 week) of first lobe in the second TACE cycle.

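### Radiology Charter 4.3 does not tie the treated territory to a TACE cycle, so the treated-area response read cannot reliably apply secondary objective v, which turns on whether liver was previously treated

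*Combined protocol and SAP*

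**What the plan says.** Protocol section 2, secondary objective v, defines progression for ORR-T: "In this evaluation progression is defined as new/continued tumor growth in the treated area(s) of the liver or extrahepatic spread". It then adds that new "tumor growth within an area of the liver not previously treated will not be considered progression". Protocol 11.5.5 bases the analysis on the Central Reviewers' "assessment of response in the treated areas of the liver only" and adopts methods like those for ORR. Under 11.5.2 those methods use the last post-TACE liver MRI and compare the arms by Fisher's exact test. Charter 4.2 likewise takes overall response at the last available assessment.

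Charter 4.3 describes the regional read. On the endpoint: "This is defined as the tumor response observed in the liver territory that has actually been treated with chemoembolization". On timing: "This analysis will be performed after the completion of the radiology review for the overall tumor response assessment for a given subject". Readers are given the baseline and timepoint 1 images, their locked forms, and a blinded form from the radiologist who did the TACE procedure (singular), with "identification of the arterial branches that were embolized during the treatment". Then "The independent radiologist will mark each lesion identified during the previous analysis as located within the treated territory" or in liver that was not embolized. Target, non-target and new lesions are all marked.

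**The concern.** Objective v depends on sequence. The same new lesion is progression if its territory had already been embolized when it arose, and is not progression if it had not. Charter 4.3 asks only whether the lesion lies inside or outside the embolized territory. It does not say whether that territory is the one embolized by a given MRI, at the first procedure, or over the whole treatment.

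The territory can change during the study. Protocol section 5 allows up to three cycles and counts two embolizations as one cycle in bilobar disease. Appendices C and E call for selective catheter placement where possible, so untreated liver will often remain. Under 7.4, "A second TACE cycle is required for all patients" unless the investigator judges it unsafe, and Charter 4.1 says this holds whatever the response read. The withdrawal criteria list extrahepatic progression but not intrahepatic progression. A patient with a new lesion outside the treated area can therefore go on to have that area embolized.

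ORR-T exists to separate local effect from new disease elsewhere. If the territory is undefined in time, identical patients can be classified differently, and a named secondary comparison between the arms rests on whichever reading is adopted.

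**Working it through.** The documents state no ORR-T rate, power or sample size, so there is no plan figure to reproduce. The check applies each reading of Charter 4.3 to three cases and compares the mark with objective v.

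**Readings**
- A: branches pooled over all cycles.
- B: branches from the first procedure only, read with baseline and timepoint 1 images.
- C: branches embolized before the MRI at which the lesion is first seen.

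**Cases**
1. A new lesion at MRI 1 in territory first embolized in cycle 2. Objective v: area not previously treated, so not progression.
2. Bilobar disease, with a baseline lesion in the second lobe, embolized in cycle 1 before MRI 1 (Protocol 7.2, 7.3). The lesion belongs to the treated area.
3. A new lesion at MRI 3 in territory first embolized in cycle 2. Objective v: area previously treated, so progression.

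| Case | Objective v requires | A: pooled | B: first procedure | C: embolized before that MRI |
|---|---|---|---|---|
| 1 | outside | inside (wrong) | outside (right) | outside (right) |
| 2 | inside | inside (right) | outside (wrong) | inside (right) |
| 3 | inside | inside (right) | outside (wrong) | inside (right) |

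Only C agrees in all three, and nothing in Charter 4.3 provides for it. The readers could not easily supply it themselves. Their locked forms show the timepoint at which a lesion first appeared. But Charter section 3 blinds them to exam dates, and the embolized-branch form is not described as saying in which cycle a branch was embolized.

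Reading B has a second difficulty. Timepoint 1 images cannot support a response at the last MRI when the patient had a second or third cycle, yet Protocol 11.5.2 and 11.5.5 imply that time point.

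**Illustrative size under reading A.** Let p be the true ORR-T and q the share of treated-area responders who have a case 1 lesion. If each is reclassified as progression, the loss in percentage points is 100 × p × q, and the number of patients per arm is 255 × p × q (255 per arm from Protocol 11.2). The values of p and q are assumptions. The upper p borrows the 77% overall mRECIST response at 6 months that the Protocol background quotes from an Italian study, which is not an ORR-T figure.
- p = 0.40, q = 0.02: 0.8 points; 255 × 0.008 = 2.0 patients.
- p = 0.60, q = 0.05: 3.0 points; 255 × 0.030 = 7.7 patients.
- p = 0.77, q = 0.10: 7.7 points; 255 × 0.077 = 19.6 patients.

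**The case against.** The strongest reply is that the Charter is silent, not wrong. It never says that a lesion is marked only once, that there is one form per patient, or that territory is pooled. The singular procedure and the timepoint 1 images point, if anything, to a first-cycle reading, under which the case 1 lesion is correctly marked outside. Section 4.3 also states no progression rule of its own, so objective v still governs. Any misclassification applies to both arms, with readers blinded to treatment, and ORR-T is only a secondary endpoint.

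Much of this stands. A reader might infer that the Charter prescribes a single mark against a cumulative map, and so that every later-embolized new lesion becomes treated-area progression. The text does not support that: pooling is one possible reading.

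Nor do the documents establish that such a patient is a progressor at the end. Appendix G makes the appearance of a new lesion progression, but response is taken at the last MRI. Nothing says how to class a lesion that was new at MRI 1 and shows no enhancement at the last MRI. Section 7.4 also does not require cycle 2 to embolize a new lesion.

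The reply does not remove the gap. The first-cycle reading rescues case 1 but fails cases 2 and 3 and conflicts with the last-MRI analysis. That objective v governs does not help if the readers are not given what they need to apply it.

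**Conclusion.** The point holds as a gap in the specification. Charter 4.3 does not link treated territory to a cycle, the endpoint definition needs that link, and neither a pooled map nor a first-procedure map delivers the endpoint in every case. A pooled map can count new disease in previously untreated liver as local failure. A first-procedure map omits territory that was treated.

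The size is unknown. The 0.8 to 7.7 points above rest on assumed rates, on the pooled reading, and on the new lesion still counting as progression at the last MRI. They should not be read as an estimate of bias. A reader might conclude that ORR-T will be understated, or that the comparison between arms is biased. The documents support neither: the direction depends on the reading adopted, and nothing indicates a difference by arm. Overall survival, the primary endpoint, is unaffected. The change is worth making because ORR-T is a named secondary objective and the remedy is cheap.

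**What to change.** Amend Charter 4.3 in three respects:

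1. Have one embolized-branch form completed per procedure, labelled by cycle and lobe but carrying neither arm nor dates, so that blinding is kept.
2. Classify each new lesion against the territory embolized before the MRI at which it first appeared. State that a new lesion outside that territory is not ORR-T progression, even if it is embolized later.
3. Show readers all post-baseline timepoints, so that the regional read matches the last-MRI analysis in Protocol 11.5.2 and 11.5.5 and Charter 4.2.

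The cost is Charter wording, a few more forms per patient and slightly more reading work. No extra reader or scan is needed.
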